9.3. Stratification and Treatment Assignment

Randomization will be performed according to a randomization schedule developed by the sponsor or sponsor's representative after the subject has signed the Informed Consent and prior to the surgical procedure. The clinical database will contain the randomization distribution system which will be used for this study.

Individuals who are randomized and receive the study treatment will be considered study (treated) subjects; only data from study (treated) subjects will be included in endpoint analysis.

Patients will be randomized 1:1 to either Xpede™ Bone Cement or Mendec bone cement. The sequence of treatments will be randomly permuted in blocks of 2 or 4 patients per block. The blocked randomization will be centralized and schedules will be created by the study statistician using statistical software. The randomization will be performed by the center via the EDC system (Oracle Clinic). To minimize the selection bias, the randomization procedure for this study will use the site (3 sites), the number of vertebral to be treated (1,2 or 3) and the type of procedure (2 procedure: VP and BKP) as stratification factors, so that there will be a separate permuted block randomization list for each stratum (18). This guarantees treatment balance within strata.

9.4. Baseline

Informed consent must be obtained prior to performing any study-specific procedure.

The following information will be collected at baseline:

- Demographic data
- Medical history,
- General physical examination
- MRI
- Imaging: A/P x ray imaging
- Concomitant medication
- All Adverse Events
- **Subject will complete:**
 - a.NRS
 - b.Quality of life questionnaires: SF-36 v2
 - c. Performance Status: Oswestry Disability Index (ODI) v2.1a:

Spinal disability will be assessed with the ODI questionnaire. The ODI is registered with the International Consortium for Health Outcome Measures as a standard outcome measure⁴. It is specific for spinal disorders and considered as the “gold standard” by several systematic reviews^{5 6 7}, and recent surgery guidelines⁸ and has been used in several studies of spinal metastases⁵.

9.5. Prior and Concomitant Medications

All medication therapy for optimal medical care will be given during the study period at the discretion of the physician(s). The specific concomitant medications listed below should be documented as concomitant medication.

- **Analgesic(s)** frequency and dose in past 24-hours will be recorded. All pain management (including but not limited to Nonsteroidal anti-inflammatory drugs (NSAIDs), acetaminophen, acetyl salicylic acid, tramadol, cannabinoids) will be collected. All opioid analgesics will be converted to oral morphine equivalent doses (OMED). Non-opioid analgesics will be counted as zero for OMED and will be analyzed separately.
- **Concurrent Osteoporosis medication(s):** Study subjects who have concurrent osteoporosis will be treated with antiresorptive therapy (e.g., bisphosphonates, parathyroid hormone (PTH), calcitonin), calcium and vitamin D as needed according to standard of care.

9.6. Procedure day

The following information will be collected during the procedure:

⁴ Fairbank JC. Why are there different versions of the Oswestry Disability Index? J Neurosurg Spine. 2014 Jan;20(1):83-6.

⁵ Fairbank JC, Pynsent PB. The Oswestry Disability Index. Spine (Phila Pa 1976). 2000 Nov 15;25(22):2940-52; discussion 2952. Review

⁶ Johnsen LG, Hellum C, Nygaard OP, Storheim K, Brox JI, Rossvoll I, Leivseth G, Grotle M. Comparison of the SF6D, the EQ5D, and the oswestry disability index in patients with chronic low back pain and degenerative disc disease. BMC Musculoskelet Disord. 2013 Apr 26;14:148.

⁷ Gum JL, Glassman SD, Carreon LY. Clinically important deterioration in patients undergoing lumbar spine surgery: a choice of evaluation methods using the Oswestry Disability Index, 36-Item Short Form Health Survey, and pain scales: clinical article. J Neurosurg Spine. 2013 Nov;19(5):564-8

⁸ Ghogawala Z, Resnick DK, Watters WC 3rd, Mummaneni PV, Dailey AT, Choudhri TF, Eck JC, Sharan A, Groff MW, Wang JC, Dhall SS, Kaiser MG. Guideline update for the performance of fusion procedures for degenerative disease of the lumbar spine. Part 2: assessment of functional outcome following lumbar fusion. J Neurosurg Spine. 2014 Jul;21(1):7-13

- Overall duration of the study procedure (skin to skin)
- Fluoroscopy duration
- Level(s) treated
- Type of anesthesia utilized
- Approach: unilateral versus bilateral BKP/VP
- BKP data including Balloon inflation volumes and pressures
- Kyphon® Xpede™ Bone Cement/Mendec volume
- Cement delivery system use
- All Adverse Events/Device Deficiencies
- Cement extravasation
- Inpatient versus outpatient status
- Length of stay

9.7. Follow up visits

Information collected post-treatment at 1 day and 3 and 6 months **onsite follow-up** visits for all subjects by the Investigator (or, if delegated, the Study Nurse/Coordinator) includes the following:

- Concomitant medications
- Re-intervention at initially treated level(s), if applicable
- Imaging: A/P x ray imaging will be collected at onsite follow-up visits
- All adverse events/device deficiencies
- Subject will complete:
 - a.NRS score
 - b.Quality of Life questionnaires: SF-36 v2
 - c. Performance Status: ODI v2.1a

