9.12. Deviation Handling

A deviation is defined as an event within a study that did not occur according to the CIP or the Clinical Trial Agreement. Prior approval by Medtronic is expected in situations where the investigator anticipates, contemplates, or makes a conscious decision to deviate. Prior approval is not required when a deviation is necessary to protect the life or physical well-being of a subject in an emergency or in unforeseen situations beyond the investigator's control (e.g., subject failure to attend scheduled follow-up visits, inadvertent loss of data due to computer malfunction or inability to perform required procedures due to subject illness).

All study deviations must be reported on the Case Report Form regardless of whether medically justifiable, pre-approved by Medtronic, an inadvertent occurrence, or taken to protect the subject in an emergency. The description of the deviation and justification must be documented.

Once a deviation has been identified it should be reported to Medtronic as soon as possible. Deviations may be identified through numerous sources, including but not limited to: telephone conversations, site monitoring, subject record, or data review.

It is the site's responsibility to report deviations in compliance with their EC/IRB policies and/or local laws.

For medically justifiable conditions which preempt a subject's ability to complete a study-required procedure, it may be permitted to complete only one deviation which will apply to all visits going forward. This may also apply for other unforeseen situations (e.g., the subject permanently refuses to complete a study required procedure and the data will not contribute to the primary end point analysis). However, prior approval from Medtronic is required for such situations.

In the occurrence of a corrupted device interrogation file, Medtronic may request a deviation to document that a readable interrogation file is unavailable. Deviations for missing device interrogation file(s) and missing or incomplete electrical testing at the same visit may be reported on one deviation CRF.

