9.13. Subject Withdrawal or Discontinuation

Every attempt should be made to follow all treated subjects through study closure.

Upon exiting from the study, no further study data will be collected or study visits will occur for the subject. No study specific medical care will be provided for subjects after the study has been completed and subject will be treated according to the standard routine practice after the study period.

All data available through the time of the subject's exit will be used for analysis. In the event of study exit, the investigator should discuss with the subject the plans for future care and treatment. The investigator should explain that the subject will continue to receive standard medical care. Alternative treatment, such as medication options, or follow-up through standard of care procedures instead of study procedures, and medical consequences should also be discussed. The investigator must notify the subject of any significant new findings that may become available during the course of the study, which are pertinent to the safety and well-being of the subject.

Exit

Subjects may be exited from the study for any of the following situations:

- Subject does not meet inclusion/exclusion criteria and has not been treated
- No BKP or VP attempted
- Procedure attempted but no bone cement was injected
- Subject chooses to withdraw from the study
- Investigator deems withdrawal necessary (medically justified or inclusion/exclusion criteria not met, failure of subject to maintain adequate study compliance)

In the event that a subject is exited from the study prior to study closure, all efforts should be made to continue following the subject until all unresolved procedure or product related adverse events are resolved or they are ongoing and no further actions will be taken.

Lost to Follow-up

In the case that the subject is determined to be lost to follow-up, details of a minimum of three attempts and the method of attempt (e.g., one letter and two phone records or two letters and one phone record) to contact the subject must be recorded. In addition, the requirements set by the governing EC/IRB for subjects lost to follow-up must be followed.

10. Risks and Benefits

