7.12. Visit windows

The visit windows for this study were defined in the table below. The days should be counted from the day of the study procedure.

For endpoints which can be collected remotely and are filled by patient (e.g., NBS, SF-36, ODI questionnaires), follow-up visit should be performed as closely to the target day as possible (± 2 weeks are allowed for the last two follow up visits).

For the endpoints which require assessment on site and X-ray/MRI assessment (e.g., vertebral body angle and vertebral body height), the follow-up visits can be completed at any time during the visit window.

Visit name	Target day	Endpoints/assessments which can be done remotely	Endpoints/assessments which require on-site visit
Baseline and randomization	\leq Day 0		
Study Procedure	Day 0		
1 Day post-operative	Day 1	Day 1 – Day 7	Day 1 – Day 7
3 months postoperative	Day 90	Day 8 – Day 135	Day 8 – Day 135
6 months postoperative	Day 180	Day 136 – Day -365	Day 136 – Day 365

Note: In case of missing assessments within the visit windows, clinical judgment could lead to acceptance/rejection of some measurements out of windows.

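### The protocol collects follow-up NRS only at on-site visits while the SAP treats it as remotely collectable, so the 6-month NRS of a patient who cannot attend is at risk of being missing

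*Protocol*

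**What the plan says.** **Where NRS is collected.** Protocol 9.7 lists NRS, SF-36 and ODI among the items gathered at "1 day and 3 and 6 months onsite follow-up visits for all subjects". Neither 9.7 nor the schedule in Table 5 (section 9.1) mentions telephone, post or electronic completion. SAP 7.12 takes a different view: "For endpoints which can be collected remotely and are filled by patient (e.g., NBS, SF-36, ODI questionnaires" are given their own column in the visit-window table, beside a column for assessments that need attendance.

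**What happens when a patient does not attend.** Protocol 9.12 gives "subject failure to attend scheduled follow-up visits" as an example of an unforeseen situation that needs no prior approval as a deviation. For medical conditions that prevent a required procedure, "it may be permitted to complete only one deviation which will apply to all visits going forward", with sponsor approval. The same section extends this to refusal, but its example is a case where "the subject permanently refuses to complete a study required procedure and the data will not contribute to the primary end point analysis".

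**Exit.** Under Protocol 9.13, "Upon exiting from the study, no further study data will be collected or study visits will occur for the subject". Exit is permissive, and one possible ground is "failure of subject to maintain adequate study compliance". After exit, "all efforts should be made to continue following the subject until all unresolved procedure or product related adverse events are resolved"; no equivalent is given for efficacy questionnaires.

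**Analysis.** Protocol 13.4 uses one NRS measure per patient. SAP 7.9.1.1 makes change from baseline to 6 months the primary NRS analysis. SAP 7.4 leaves a missing outcome unimputed. SAP 7.1.2 counts a missing 6-month assessment as a major deviation, and SAP 7.1.3 requires completed 6-month follow-up for the Per Protocol Set.

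**The concern.** Sites work from the protocol, and the SAP cannot by itself give them a way to collect data. Consider a patient who at 6 months cannot travel, or declines the X-ray, but would still give a 0 to 10 pain score. A site following 9.7 literally records a missed visit and has no instruction to ask for the score. Its absence would come from the collection route, not from the patient's unwillingness to answer.

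NRS is one of two co-primary endpoints, needs no imaging, and is the endpoint that sets the sample size. Its value at 6 months is not imputed. Patients who cannot travel may also differ in pain from those who can. If so, the missing values would be informative as well as costing precision. That is plausible, but the documents give nothing with which to measure it.

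**Working it through.** **1. Passages side by side**

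| Question | Protocol | SAP |
|---|---|---|
| Where is follow-up NRS collected? | On site, all subjects (9.7) | Can be remote (7.12) |
| Is a missed visit an exit? | No, a deviation (9.12) | Missing 6-month assessment is a major deviation (7.1.2) |
| Is another route to NRS prescribed for a non-attender? | None stated | Assumed, not specified |
| Do questionnaires continue after exit? | No; only related unresolved adverse events are followed (9.13) | Data up to last collection are used (7.1.3) |
| Is a missing 6-month NRS imputed? | Method left open (13.4) | Outcome not imputed (7.4) |

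The first row is a contradiction. The third row is the practical gap: the patient remains enrolled, but no one is told to obtain the value.

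**2. The plan's own sample size**

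Inputs from Protocol 13.1.2: margin 1.5, SD 3.27, expected difference 0 (3.5 in each arm), one-sided alpha 0.025, power 0.80, allocation 1:1, loss 15%.

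With n evaluable patients per arm, noncentrality = 1.5 / (3.27 × √(2/n)) on 2n − 2 degrees of freedom. Power is the probability that this noncentral t exceeds the 97.5th percentile of the central t.

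- n = 76: 1.5 / (3.27 × √(2/76)) = 2.83, power 0.802. Required: 2 × 76 = 152, as stated.
- 152 / 0.85 = 178.8, so 179, rounded up to 180 to be divisible by 18, as stated.
- With 180 randomised, 180 × 0.85 = 153 are evaluable, one more than the 152 needed.

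**3. What remote NRS could be worth**

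The recoverable share is not in the documents. The shares below are assumptions. The starting point is the planned loss of 0.15 × 180 = 27 patients.

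| Assumed share of the 27 recovered | Evaluable | Per arm | NRS power |
|---|---|---|---|
| None | 153 | 76.5 | 0.805 |
| One third (9) | 162 | 81 | 0.827 |
| One half (13.5) | 166.5 | 83.25 | 0.837 |
| All (upper limit) | 180 | 90 | 0.864 |

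**4. If loss is higher than planned**

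Protocol 13.2.2 budgets 20% loss for the angle endpoint. If NRS depends on the same visit and 20% applied to it, 180 × 0.80 = 144 would be evaluable and NRS power would be 0.780. Recovering one third of those 36 gives 156 evaluable and power 0.812.

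**5. The other co-primary**

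Angle needs an X-ray, so remote contact recovers none of it. At 20% loss, 243 × 0.80 ≈ 194 levels remain against the 160 required. Power is about 0.87 with margin 2.5 and SD 5.6, treating levels as independent as the protocol's calculation does.

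**The case against.** A reader might infer that exit is all-or-nothing, so that a patient who merely stops travelling leaves the study and forfeits the NRS co-primary. The documents do not support that. Protocol 9.12 treats non-attendance as a deviation. The exit list in 9.13 is permissive and does not name declined travel; the nearest item is investigator-judged non-compliance. Section 9.13 also asks sites to try to follow every treated subject to closure.

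Nor is the NRS certain to be lost:

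- Section 9.7 does not forbid remote completion.
- Table 5 has an Unscheduled column, without a window, in which NRS, ODI and SF-36 are marked.
- The SAP 7.12 table accepts 6-month data from Day 136 to Day 365, although its text gives ±2 weeks for patient-completed endpoints, and it allows judgement on out-of-window values.
- The MMRM named in SAP 7.2 could use a patient's earlier NRS values, although Protocol 13.4 describes one measure per patient.

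The power gains are also easily over-read. The 15% is loss to follow-up, and 9.13 requires at least three documented contact attempts before that label applies. Part of it will be patients nobody can reach, so one third or one half recovery has no support in the documents. The remote and on-site columns in SAP 7.12 carry the same day ranges, so the separate column changes no window.

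All of this stands, and it limits the consequence. It does not remove the contradiction between 9.7 and SAP 7.12, and none of these routes instructs a site to obtain the 6-month NRS from a patient who will not attend. The standing-deviation example for refusal is confined to data outside the primary endpoint analysis, so it does not settle the matter for either co-primary.

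**Conclusion.** The concern holds in limited form. The protocol provides only on-site collection of follow-up NRS, the SAP assumes remote collection is available, and the passages must be reconciled. A non-attender stays enrolled, but the 6-month NRS is at risk of being missing and would not be imputed.

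The size is modest and uncertain. On the plan's SD, margin and zero true difference, NRS power is about 0.80 at 15% loss with no recovery. The illustrative recoveries of one third and one half add about 2 and 3 percentage points (0.827 and 0.837 against 0.805). The true gain could be close to nil if most losses are unreachable patients. It matters more if loss exceeds 15%, because the plan has only one evaluable patient to spare. Trial success needs both co-primaries, and the angle endpoint gains nothing. Bias from selective loss is possible but cannot be quantified from the documents. This is a worthwhile low-cost improvement, not a defect that threatens the trial's validity.

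**What to change.** Amend Protocol 9.7 and 9.13, and align SAP 7.12, as follows:

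- A patient who cannot or will not attend the 3- or 6-month visit is asked remotely for NRS, ODI, SF-36 and an adverse event review, within the protocol's ±2-week window, and stays in the study. Exit from data collection applies only if this too is refused.
- The contact is made by the blinded site personnel already provided for in Protocol 9.9.
- The eCRF records the mode of collection. Remote NRS values enter the primary FAS analysis, with a sensitivity analysis excluding them.
- Protocol 14.5, which treats the patient-completed questionnaire as the source document, states how remote responses are documented.
- SAP 7.1.2 and 7.1.3 state whether a remote response counts as a completed 6-month visit for the Per Protocol Set.
- NBS in SAP 7.12 is corrected to NRS.

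The cost is a short protocol amendment, matching SAP edits, one eCRF field and a source-documentation rule. No patients are added, and sites already make contact attempts under 9.13. The downside is that a few NRS values come by a different mode; the recorded mode and the sensitivity analysis let the sponsor check its influence.

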9.8. Radiography assessment

Radiological measurements will be made both by the blinded site personnel and by a centralized, independent radiologist (corelab).

A. Vertebral Body Height

Vertebral body height should be assessed at Pre-Operative, 1 days, 3-, 6-month.

Vertebral Body Height in the lateral projection will be measured at each treated vertebra as well as the next adjacent vertebrae (superior and inferior) without fracture and reported in millimeters. Vertebral Body Height is the distance between comparable points on the superior and inferior

endplates of the vertebral body at the posterior (Hp), midline (Hm) and anterior (Ha) locations as shown in Figure 3.

Notes about Adjacent Vertebral Body Height Measurements:

Note 1: The normal estimated pre-fracture height of the treated vertebra will be based on the average of the nearest adjacent non-fractured vertebrae (see Figure 4 below). The reviewer will record the level of the nearest non-fractured level superior to and inferior to the treated level.

Note 2: When L5 is the treated vertebra, the estimated pre-fracture (predicted) height of L5 will be based on L4 or the nearest superior non-fractured level. The height of S1 is not suitable as a predictor of the pre-fracture height of L5.

Note 3: The height of the nearest adjacent, non-fractured, vertebrae may be calculated at a single time point and used for all measurements at other time points. In general, the adjacent level vertebral heights will be obtained at the Pre-Operative time point from standing neutral lateral x-rays.

Note 4: In some cases, the superior or inferior adjacent vertebra may be poorly visualized at the Pre-Operative visit due to inadequate image quality. In this situation, the adjacent vertebra may be excluded from the analysis, or a subsequent visit, e.g. Post-Operative, may be used to obtain a reliable measurement of the adjacent vertebral body height.

- 1) Posterior height (Hp) is obtained by placing a vertical line along the dorsal surface of the vertebral body from the posterior point of the superior vertebral body endplate to the posterior point of the inferior endplate.
- 2) Midline height (Hm) is obtained by placing a vertical line along the midline of the vertebral body from the midpoint of the superior vertebral body endplate to the midpoint of the inferior endplate. The height will be measured between the two opposing endplates. If the vertebra is tilted or image obliquely giving a double endplate appearance in the radiograph, the vertical midpoint of the intact endplate lines will be used as the reference point for measurement.
- 3) Anterior height (Ha) is obtained by placing a vertical line along the ventral surface of the vertebral body from the anterior point of the superior vertebral body endplate to the anterior point of the inferior endplate.

[figure not shown]

Figure 3: Vertebral Body Height

[figure not shown]

Figure 4: Examples of Using the Next Adjacent Non-Fractured Vertebra(e)

Magnification Adjustment

Vertebral Body Height will be adjusted for variation in image scale by the use of a magnification marker. The clinical sites are responsible for ensuring the use of magnification markers, provided by Medtronic, on all lateral images. Image readers will measure the diameter of the marker and the

Medtronic Confidential

ratio of the measurement diameter to the true diameter will define the magnification of the image. This magnification will be used to adjust all vertebral body height measurements to a common scale at each visit. If the marker is not present or not measurable at a particular visit, the reviewer may use a stable anatomical feature common with a calibrated visit to make a similar adjustment for scale differences.

B. Vertebral Body Angle

Vertebral body Angle should be assessed at Pre-Operative, 1 days, 3-, 6-month.

- 1) Two lines will be drawn, the first line along the superior endplate of the fractured vertebral body and the second line along the inferior endplate of the fractured vertebral body for each fractured vertebral body.
- 2) The angle between these two lines will then be measured. This is shown in Figure 5. Negative angles will be associated with a kyphosis (wedge-shaped) vertebral body; positive angles will be associated with lordotic (fish-mouthed) vertebral body. A zero-degree angle will indicate that the vertebral endplates are parallel.

[figure not shown]

Figure 5: Example of Measuring Vertebral Body Angle of a Treated Vertebra Vertebral Body Angle of Index Fracture

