7.9.2. Secondary Endpoints

The secondary endpoints include:

- Change of NRS score from baseline at 1 day and 3-month visit
- Change of ODI (see section 10.3 for details) from baseline at 1 day, 3-month visit and 6-month visit
- Change of SF-36 (see section 10.3 for details) from baseline at 1 day, 3-month visit and 6-month visit
- Change of Vertebral body height restoration (see section 10.3 for calculation) at 1 day and 3-month visit and 6-month visit
- Change of Vertebral body angle from baseline at 1 day, 3-month visit and 6-month visit

The analysis will use multiple data points per patient (1 day, 3 months, 6 months). Assuming not completely independence among measures within same patient the analysis will be performed by means of Generalized Estimating Equation (or mixed models for repeated measures) using patient as the subject ID. The model will have the NRS, ODI, SF-36 (PCS, MCS), height restoration and angle as dependent variables (for each model) and baseline value, arm as explanatory variables. All assumptions for regression models will be assessed by viewing plots of the residual values. Potential confounders could be included in the model to adjust estimates.

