10.3. Secondary Endpoint calculation

10.3.1. Vertebral Body Height Restoration

The vertebral body height restoration will be expressed as Absolute Height Restored (AHR) for anterior, mid and posterior defined as:

AHRA: $Ha_{\text{post-treatment}} - Ha_{\text{at treatment}}$: where the anterior (Ha) vertebral body height is measured in millimeters (mm)

AHRM: $Hm_{\text{post-treatment}} - Hm_{\text{at treatment}}$: where the mid (Hm) vertebral body height is measured in millimeters (mm)

AHRP: $Hp_{\text{post-treatment}} - Hp_{\text{at treatment}}$: where the posterior (Hp) vertebral body height is measured in millimeters (mm)

Note that *change from baseline treatment to post-treatment* will be calculated as the difference between post-treatment in treated level and the baseline treatment in nearest superior, adjacent, non-fractured level.

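### The SAP height model names only baseline and arm, leaving unused the pre-fracture height that the protocol already collects; precision of a secondary endpoint may be lost, by an amount that depends on assumptions

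*Protocol*

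**What the plan says.** **Collection.** Protocol 9.8, part A has posterior, midline and anterior heights read at each treated vertebra and at the adjacent non-fractured ones. Note 1 states the purpose: "The normal estimated pre-fracture height of the treated vertebra will be based on the average of the nearest adjacent non-fractured vertebrae". Note 2 uses the superior side only when L5 is treated. Note 3 covers timing: "In general, the adjacent level vertebral heights will be obtained at the Pre-Operative time point from standing neutral lateral x-rays". Note 4 lets a poorly seen neighbour be left out or read from a later visit. The readers are named in the same section: "Radiological measurements will be made both by the blinded site personnel and by a centralized, independent radiologist (corelab".

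**Outcome.** SAP 10.3.1: "The vertebral body height restoration will be expressed as Absolute Height Restored (AHR) for anterior, mid and posterior". Each formula is post-treatment height minus height at treatment, in millimetres. A note below the formulas defines the change differently: post-treatment height of the treated level minus the baseline height of the nearest superior non-fractured level.

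**Model.** SAP 7.9.2 fits GEE or a mixed model with "height restoration and angle as dependent variables (for each model) and baseline value, arm as explanatory variables". It adds: "Potential confounders could be included in the model to adjust estimates". The Note 1 estimate is not named anywhere in the SAP.

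**The concern.** Pre-operative height mixes two things: how large the vertebra was and how much of it was lost. A small vertebra with little loss and a large one collapsed to the same height share a baseline value, yet the second has more millimetres to regain. Only a reference height separates them. Room to recover should differ between patients, because the intended population in Protocol 7.4 includes microfractures with no obvious height loss. Randomisation is stratified by site, number of levels and procedure (Protocol 9.3), not by vertebral size or degree of collapse.

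At stake is the width of the confidence interval for the arm difference in height restored. Chance imbalance in size or collapse would also remain in that estimate when a covariate already on file could remove part of it.

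**Working it through.** **The plan's own figure.** There is none to reproduce. No SD, margin, power or sample size is stated for height. The 180 subjects come from the NRS endpoint (SAP 6.1).

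**Worked case (all inputs assumed).** Let R be true pre-fracture height, D height lost, B = R − D pre-operative height, and R\* = R + u the Note 1 estimate. Height restored is Y = f·D + e, with R, D, e and u independent. Take f = 0.4, SD(R) = 3, SD(D) = 5, SD(e) = 3 and SD(u) = 1 mm.

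1. Var(Y) = 0.4² × 25 + 9 = 13.
2. Covariate B only: Cov(Y,B) = −0.4 × 25 = −10 and Var(B) = 9 + 25 = 34. Residual variance = 13 − 100/34 = 10.06.
3. Covariates B and R\*: Var(R\*) = 10, Cov(B,R\*) = 9, Cov(Y,R\*) = 0. Residual variance = 13 − 100 × 10/(34 × 10 − 81) = 13 − 3.86 = 9.14.
4. Ratio = 9.14/10.06 = 0.909. Standard error reduction = 1 − √0.909 = 4.7%.

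**Range of the same model.** 108 combinations: f 0.2 to 0.6, SD(R) 2 to 4, SD(D) 3 to 5, SD(e) 2 to 3, SD(u) 0 to 1.5 mm. The interval narrows by 0.3% to 27%, median 4.6%, interquartile range 1.9% to 8.6%.

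**Simulation with recovery as a share of the loss (all inputs assumed).** 200,000 vertebrae in each of 12 scenarios:
- pre-fracture height mean 25 mm, SD 2, 3.5 or 5 mm
- mean loss 20% or 35% (SD 12%)
- 40% of the loss restored (SD 15% or 30%)
- reading error 1 mm, or 1.5 mm for pre-fracture height

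Adding pre-fracture height to baseline height gives residual variance ratios of 0.61 to 0.96. Standard error reduction is 1 − √0.96 = 2% to 1 − √0.61 = 22%.

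**When the gain disappears.**
- *Recovery unrelated to height lost.* In the worked model f = 0, so Cov(Y,B) = 0 and neither covariate helps. In the simulation the ratio is 0.98 to 1.00.
- *The SAP 10.3.1 note governs, and its own baseline is the covariate.* With R\* as the reference, the outcome is B + Y − R\* and its baseline is B − R\* = −(D + u). In the worked case, residual variance given that baseline = 13 − 100/26 = 9.15. Adding R\* gives 9.14, a ratio of 0.998. In the simulation the further variance cut is about 0.3% to 5%, median 1%.
- *The note governs, and the deficit is replaced by pre-operative height plus Note 1 height.* The superior level then stays in the outcome without being in the covariates. Residual variance rises, by a ratio of 1.4 to 2.5 under proportional recovery. The outcome must therefore be settled before the covariates.

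**The case against.** Four objections have force.

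- **The outcome is not settled.** A reader might infer that the loss arises under either definition in SAP 10.3.1, or that the baseline term adjusts for nothing because restoration is zero for everyone before treatment. The second holds only if the formula governs and the term means the restoration variable's own baseline. Under the note, that baseline is the height deficit, which already carries room to recover. This stands, and it limits the point to the formula reading.
- **The size is assumed.** Both calculations build in recovery proportional to loss, and nothing in the documents says that this holds. This stands; the range has to include roughly zero.
- **The model is not closed, and pooling is not stated.** SAP 7.9.2 permits further covariates, but names none, so nothing is pre-specified. A reader might also infer that the model pools all treated vertebrae. SAP 7.9.2 lists only the three visits as the repeated data points and does not say how several levels in one patient enter the height model.
- **A strict covariate rule could cost more than it gains.** Because of Note 4, some pre-operative neighbours will be unreadable. Dropping about 9% of vertebrae would cancel a 4.6% standard error gain, since 0.954² = 0.91. A share-of-loss ratio is also unstable when little height was lost. Both are answered by the form of the fix.

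A reader might go further and infer a biased arm comparison or a threat to trial success. The documents support neither. Allocation is randomised, height is a secondary endpoint without margin or power, and success depends on NRS and angle alone (Protocol 13.4; SAP 7.9.1).

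**Conclusion.** The point holds as a modest matter of efficiency. The protocol yields a pre-fracture height that is generally pre-operative, and the pre-specified height model does not use it. If height restored is the treated vertebra's own change, and recovery is roughly proportional to height lost, including it would lower the standard error by about 2% to 22% on the simulated inputs. The wider analytic grid puts the typical gain near 5%. If either condition fails, the gain can be close to nothing. All height inputs are assumptions. Only the precision of a secondary endpoint is affected; the 180 subjects and both primary analyses stay as they are.

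**What to change.** 1. **SAP 10.3.1.** Reconcile the formula with its note: use change from baseline at the treated level as the outcome, and Protocol 9.8, Note 1 (with Note 2 for L5) as the only rule for the reference height.
2. **SAP 7.9.2.** For the anterior, mid and posterior models, define the baseline term as the pre-operative height of the same treated vertebra at that location. Add the Note 1 pre-fracture height at that location as a fixed covariate.
3. **Unreadable films.** Take the reference from pre-operative films. If one neighbour is unreadable, use the other. If neither is readable, apply a stated simple imputation of the covariate, made without reference to arm or outcome, so that no vertebra is dropped.
4. **Share of lost height restored.** If reported, keep it descriptive and state a minimum loss for inclusion.

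The cost is SAP wording, one extra covariate from readings already planned, and a few imputed covariate values. No new images, reads or patients are needed.
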